## 5 ANALYSIS POPULATIONS

## **Intention-to-Treat Population (ITT)**

The intention-to-treat population will comprise of all randomized participants who have at least one efficacy measurement. Participants who receive study drug but do not complete the study will be used in all analyses for which data are available. Participants who are withdrawn for further follow-up will be treated as lost to follow-up at the time that consent was withdrawn, and data will be used up to the time of study withdrawal (unless parents/guardians expressly forbid use of any collected data).

## **Safety Population**

The safety population will comprise of all randomized participants regardless of treatment received or collection of efficacy information.

#### **6 SAMPLE SIZE DETERMINATION**

To obtain a two-day difference in the primary outcome of days from randomization to discharge, from 14 days to 12 days, with a power set at 90%, a significance of 0.05, and a 5% attrition, the trial would require 587 infants per group (intervention and placebo) for a total of 1174 infants, assuming a two-tailed, non-parametric test comparing median LOS in the two groups. With a power set at 80%, under the same assumptions and significance, the trial would require 439 infants per group for a total of 878 infants. The minimum required sample size for this trial will be 878 (439 in each treatment group), but enrollment will continue until either the available supply of study drug is exhausted or expires in approximately August 2023 (accounting for full in-hospital and post-discharge follow-up), whichever comes first.

There are approximately 3000 infants born between 290/7 and 33 6/7 weeks gestation per year in the NRN. A review of 100 infants in the NICU at one of the largest centers in the NRN showed that 37% of infants within this cohort were treated with a methylxanthine. This is similar to NRN data showing that approximately 1000 (one-third) of infants receive caffeine therapy. The following table shows scenarios for approximate time to completion of the trial as a function of consent rate and NICHD center involvement:

| Consent Rate (%) | Time to Completion (mo), all sites | Time to Completion (mo), half sites |
|------------------|------------------------------------|-------------------------------------|
| 50               | 24                                 | 48                                  |
| 60               | 20                                 | 40                                  |
| 70               | 18                                 | 36                                  |
| 80               | 15                                 | 30                                  |

| Effect Size (days) | Significance | Power (%) | Attrition (%) | Sample Size |
|--------------------|--------------|-----------|---------------|-------------|
| 14 to 10           | 0.05         | 80        | 5             | 226         |
| 14 to 10           | 0.05         | 90        | 5             | 302         |
| 14 to 12           | 0.05         | 80        | 5             | 878         |
| 14 to 12           | 0.05         | 90        | 5             | 1174        |

#### 7 STATISTICAL/ANALYTICAL ISSUES

## 7.1 General Rules

All statistical computations performed and data summaries created will be accomplished using SAS 9.4 or higher. If additional statistical packages are required, these will be discussed in the study report. For summaries of study data, categorical measures will be summarized in tables listing the frequency and the percentage of subjects in each study arm; continuous data will be summarized by presenting mean, standard deviation, median and range; and ordinal data will be summarized by only presenting median and range.

## 7.2 Adjustments for Covariates

Indicator variables for the study stratification of site and gestational age will be included as covariates in most efficacy analyses performed for this study. Additionally, demographic and baseline characteristics for subjects will be compared between study arms using analysis of covariance techniques for continuous measures, Mantel-Haenszel mean score test using standardized mid-rank scores for ordinal measures, and Cochran Mantel-Haenszel chi-square tests for general association for categorical measures. If sample sizes allow, these analyses will control for the study stratification factors. If these analyses suggest that substantial differences exist among arms, the use as covariates of these parameters on which the arms differ will be explored in exploratory analyses of the efficacy data.

## 7.3 Handling of Dropouts and Missing Data

Missing data will be monitored in real-time. In the event an assessment or data form is missed, DCC staff will contact site coordinators to enter the required information from the in-hospital portion of the study as quickly as possible. For the post-hospital data collection, missing data will be queried by DCC staff to determine if the site has collected the desired information from the parents/guardians. Given that recruitment into the study and the primary outcome are all performed/collected during the initial hospital stay, it is not anticipated that there will be any missing data for the length-of-stay primary outcome.

## 7.4 Interim Analyses and Data Monitoring

Statistical interim monitoring for this trial will be conducted by the independent NRN Data Safety and Monitoring Committee (DSMC) using data and analyses provided by the NRN DCC at RTI. We recommend that the DSMC meet formally to review interim safety, efficacy, and futility, as well as other aspects of accruing data (such as enrollment, data completeness and protocol compliance) four times during the study, after 100 infants complete the eight-week follow up and then roughly after 25%, 50% and 75% of subjects complete the eight-week follow up. Formal DSMC reports will be prepared by the DCC for these meetings. These reports will include the following information:

- Brief summary of the trial design, including primary and secondary hypotheses and outcomes, study population, inclusion and exclusion criteria, recruitment, screening, randomization and study intervention procedures, and statistical considerations for trial design and analysis
- Interim monitoring plan
- Enrollment, including screening, consent, randomization, and study exit
- Completeness of data and edit queries. Baseline study population characteristics, overall and by treatment group
- Drug adherence and compliance
- Primary efficacy outcomes by treatment group
- Secondary efficacy outcomes by treatment group
- Safety outcomes, including death, by treatment group
- Protocol deviations and violations, overall and by treatment group.

These DSMC reports will be blinded, with treatments labeled as group A and group B. As per the NRN DSMC Charter, the DSMC may, however, request to be un-blinded to perform their duties. If the DSMC recommends modification or cessation of the study protocol due to safety concerns, NICHD will make the final determination.

## **Interim Safety Monitoring**

Statistical interim safety monitoring will be conducted by the DCC after 100 infants complete the eight-week follow up and then after 25% (300), 50% (600), and 75% (900) of the infants enrolled complete the eight-week follow up period. Formal safety assessment will be based on the number of sick visits, emergency room visits, apparent life-threatening event episodes or hospitalizations related to AoP. Relatively liberal Pocock safety bounds based on 5 interim safety looks at the data will be constructed to guard against any occurrence of false positives while at the same time allowing for stopping at reasonable levels of evidence. Thus, at each of these safety looks, an increased incidence of the above safety events in the caffeine group with p < 0.0158 will be considered as statistically significant evidence of harm that the DSMC can use to recommend suspension of the trial for safety reasons. In addition to the formal safety outcome, other safety outcomes collected in this trial (see section 6.3.1) will also be examined by treatment group. If a death occurs in either of the groups, the DSMC will review the cause of death and determine if the cause is linked to the study intervention. If it is deemed to be related to the intervention as an increased risk, the DSMC may recommend stopping the trial. After the DCC conducts each of these interim safety analyses, it will inform the Chair of the DSMC (or her designee) if there is any suggestion of a trend in the safety data. The DSMC Chair will then determine any future course of action, including convening a meeting of the entire panel to discuss the safety data.

## **Interim Efficacy Monitoring**

Statistical interim efficacy monitoring will be conducted by the DCC after 25%, 50% and 75% of the babies enrolled into the trial complete eight-week follow up period. At each of these interim looks, the primary outcome will be compared by (blinded) treatment group using the methods outlined in Section 9. O'Brien Fleming stopping bounds for efficacy will be used to preserve an overall Type-I error rate of 0.05 for the primary outcome. Thus, stopping bounds for efficacy will be established if p  $< 5 \times 10^{-5}$  at 25%, p < 0.004 at 50% and p < 0.018 at 75% of interim data accrual. In the event that these stopping bounds are reached, the DSMC may recommend termination of the trial for efficacy. In addition to the primary outcome, secondary efficacy outcomes collected in this trial will also be examined by treatment group.

## **Interim Futility Monitoring**

Statistical interim futility monitoring will be conducted by the DCC after 50% and 75% of the babies enrolled into the trial complete the eight-week follow up period. At each of these two looks, we will estimate conditional power, i.e., the probability to detect a statistically significant treatment effect for caffeine, given the observed data and the hypothesized treatment effect for the unobserved data. The DSMC may recommend suspension of the trial for futility if this probability is less than 15%. In addition to the conditional power analysis, the DSMC may also consider other pertinent aspects included in the interim report such as the quality of the data, protocol violations and treatment adherence, rate of enrollment, rate of attrition, in determining futility.

## Additional Data Monitoring

Additional monitoring of data for this study will occur in real-time and will include study drug and home kit reconciliation with randomization, pharmacy log reconciliation with patient administration log, missing and incomplete forms, tracking of primary and secondary outcomes, and reporting of protocol deviations and adverse events.

Page 13

Final 2022-12-12

Expedited serious adverse events will be reported per local IRB guidelines, and within 24 hours to the NRN DCC at RTI.

The trial will record side effects and any study related serious adverse events will be reported to the DSMC periodically. Expedited serious adverse events will be reported per local IRB guidelines, and within 24 hours to the NRN DCC at RTI. All protocol deviations and violations will be reported.

Infants will be monitored prospectively while in the NICU. Interim efficacy and safety will be formally evaluated by the independent DSMC.

## 7.5 Masked Data Review

A masked data review of the primary outcome and secondary outcomes for this study will be performed by the protocol team. This review will occur prior to completion of the primary analyses prior to any official unblinding. This will include a presentation of descriptive statistics (e.g., means, standard deviations, percentiles for continuous variables and counts and percentages of categorical variables) of the selected outcomes and model predictor variables.

#### 7.6 Multicenter Studies

For this multicenter study, randomization of study participants is stratified within center and by gestational age. Consequently, for all model-based primary and secondary analyses, center will be included as a fixed effect in the models. As an ancillary analysis associated with the primary outcome, we will examine descriptively whether the treatment effect varies across sites; however, no other analyses will assess site differences in treatment effect because sample sizes are inadequate to support evaluation of site-level effects.

## 7.7 Multiple Comparisons and Multiplicity

The primary hypothesis will be tested at a nominal two-sided type I error of 0.05. All p-values for any baseline and demographic characteristic comparisons, secondary outcomes, and safety parameters will be for descriptive purposes only.

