#### Interim Efficacy Monitoring

Statistical interim efficacy monitoring will be conducted by the Data Coordinating Center after 25%, 50% and 75% of the babies enrolled into the trial complete eight-week follow up period. At each of these interim looks, the primary outcome will be compared by (blinded) treatment group as per the analysis plan in section 6.2. O'Brien Fleming stopping bounds for efficacy will be used to preserve an overall Type-I error rate of 0.05 for the primary outcome. Thus, stopping bounds for efficacy will be established if  $p < 5 \times 10^{-5}$  at 25%,  $p < 0.004$  at 50% and  $p < 0.018$  at 75% of interim data accrual. In the event that these stopping bounds are reached, the Data Safety and Monitoring Committee may recommend termination of the trial for efficacy. In addition to the primary outcome, secondary efficacy outcomes collected in this trial (see section 4.2) will also be examined by treatment group.

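### Three efficacy looks are meant to preserve an overall 0.05, but the only level given for the primary test is a nominal 0.05, and no final-look threshold is stated; read literally, overall error is about 0.056

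*SAP*

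**What the plan says.** SAP 7.4, Interim Efficacy Monitoring, schedules efficacy comparisons of the primary outcome "after 25%, 50% and 75% of the babies enrolled into the trial complete eight-week follow up period". It gives the purpose of the bounds: "O'Brien Fleming stopping bounds for efficacy will be used to preserve an overall Type-I error rate of 0.05 for the primary outcome". The printed thresholds are p < 5×10⁻⁵ at 25%, then "p < 0.004 at 50% and p < 0.018 at 75% of interim data accrual". The list ends there. Protocol 6.3.3 has the same looks and bounds, and makes them advisory: "In the event that these stopping bounds are reached, the Data Safety and Monitoring Committee may recommend termination of the trial for efficacy".

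SAP 7.7, on multiplicity, gives the level for the primary test: "The primary hypothesis will be tested at a nominal two-sided type I error of 0.05". It does not mention the interim looks. SAP 9.3 describes the primary model, p-values and 95% intervals but gives no significance level. SAP 13 records no departures from the protocol.

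Two other places bear on the point. The futility rule in SAP 7.4 defines conditional power as "the probability to detect a statistically significant treatment effect for caffeine, given the observed data", so it needs a definition of significance at the final analysis. SAP 6 sets a minimum of 878 infants, "but enrollment will continue until either the available supply of study drug is exhausted or expires in approximately August 2023", so the final sample size, and with it the information fraction at each look, is not fixed in advance.

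**The concern.** A group-sequential rule with an overall level of 0.05 spends part of that level at the interim looks, so the final test must use less than 0.05. The plan prints the three interim bounds and omits the fourth. SAP 7.7 is where a reader would look for it, and the figure there is 0.05, described as nominal. In group-sequential usage that word normally means the level applied at a single analysis.

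The consequence is specific. Suppose no interim bound is crossed and the final p-value falls between about 0.044 and 0.05. SAP 7.7 read literally calls the trial positive; the overall 0.05 promised in SAP 7.4 and Protocol 6.3.3 does not. The two sections would then disagree on the primary hypothesis, and the choice between them would be made with the result in hand.

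**Working it through.** **Inputs.** From SAP 7.4 and Protocol 6.3.3: looks at t = 0.25, 0.50 and 0.75; two-sided bounds 5×10⁻⁵, 0.004 and 0.018; target overall error 0.05. From SAP 7.7: final test at two-sided 0.05, giving z = 1.960. Assumptions: information is proportional to infants, the test statistic is asymptotically normal with independent increments, and any crossing counts as a rejection. The advisory futility rule is ignored.

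**Do the printed bounds identify a final bound?** Two-sided p-values at 25 / 50 / 75 / 100%:

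| Version | 25% | 50% | 75% | Final |
|---|---|---|---|---|
| Printed in the plan | 5×10⁻⁵ | 0.004 | 0.018 | not given |
| Classical O'Brien-Fleming, 4 analyses, C = 2.024 | 5.15×10⁻⁵ | 0.0042 | 0.0194 | 0.0429 |
| Lan-DeMets spending, one-sided 0.025 form | 1.5×10⁻⁵ | 0.0030 | 0.0183 | 0.0440 |
| Lan-DeMets spending, two-sided 0.05 form | 8.9×10⁻⁵ | 0.0055 | 0.0215 | 0.0411 |
| Single constant C = 2.040 | 4.5×10⁻⁵ | 0.0039 | 0.0185 | about 0.041 |

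None of the three standard versions matches all three printed bounds. The constant 2.040 fits them after rounding, but its overall error is 0.048. With looks at 25/50/75%, every version puts the final threshold between about 0.041 and 0.044.

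**Overall error with a final test at 0.05.** The printed bounds correspond to z = 4.056, 2.878 and 2.366. With B(t) = Z(t)·√t and independent normal increments, the probability of first crossing at each look follows by recursive numerical integration:

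- 25%: 0.00005
- 50%: 0.00397
- 75%: 0.01545
- final, at p < 0.05: 0.0361

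The interim total is 0.00005 + 0.00397 + 0.01545 ≈ 0.0195. Adding 0.0361 gives an overall error of 0.0556. A simulation of 4 million null trials also gives 0.0556. Moving the printed bounds within their rounding gives 0.0552 to 0.0559.

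**Threshold that restores 0.05.** Solving for the final z with the interim bounds as printed gives z = 2.016, p = 0.0438.

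**Sensitivity to which looks are held and when** (printed bounds, final test at 0.05):

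| Looks held | Overall error | Final p giving 0.05 |
|---|---|---|
| 25, 50, 75% | 0.0556 | 0.0438 |
| 50, 75% | 0.0555 | 0.0438 |
| 75% only | 0.0546 | 0.0449 |
| 50% only | 0.0514 | 0.0486 |
| 25% only | 0.0500 | 0.0500 |
| 300, 600, 900, ending at 1,174 | 0.0552 | 0.0442 |
| 300, 600, ending at 878 | 0.0506 | 0.0494 |
| 220, 439, 659, ending at 1,174 | 0.0595 | 0.0394 |

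The last three rows assume timings. The counts 300/600/900 are those printed for the safety looks. The counts 220/439/659 are 25/50/75% of 878, followed by enrollment to the 90%-power size.

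**How often it matters.** Under the null, a final p between 0.0438 and 0.05 with no earlier crossing has probability 0.0556 − 0.0500 = 0.0056, or 0.6%. Under the design effects, with drift 1.960 + 0.842 and 1.960 + 1.282, power with the looks counted is 0.8062 at a final 0.05 against 0.7918 at 0.0438, and 0.9036 against 0.8944. The differences, 0.0144 and 0.0091, are the probability of landing in that band.

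**Conditional power.** A value of 15.0% against 0.05 corresponds to a normal deviate of 1.036. Moving the final threshold to z = 2.016 adds (2.016 − 1.960)/√(1 − t), which gives 13.2% at t = 0.50 and 12.5% at t = 0.75.

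**The case against.** The strongest reply is that the plan already states the controlling rule. A named boundary family, stated looks and an overall 0.05 imply a final bound below 0.05. SAP 7.7 does not say that the final p-value is compared with 0.05; its next sentence concerns baseline, secondary and safety p-values, so it can be read as dealing with multiplicity across outcomes and leaving the looks to SAP 7.4. On that reading 0.05 is the overall level and nothing is inflated. This is a fair reading, but it leaves the final threshold unstated, and the printed bounds do not settle it.

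Second, the bounds are advisory. The figure 0.0556 counts every crossing as a rejection; if a crossing leads to neither a stop nor a claim, the excess is smaller. That stands.

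Third, the effect is small, and under some timings almost nil: 0.0500 with a 25% look alone, and 0.0506 with looks at 300 and 600 and a stop at 878. The upper end, 0.0595, needs looks timed to 878 and enrollment on to 1,174. Both ends are assumed scenarios. They show that a fixed threshold cannot be right for every way the trial may run, so the plan needs a rule for recomputing it.

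Fourth, 0.0438 is not the only defensible value: the single-constant boundary would give about 0.041. That is true. The figure 0.0438 takes the three printed bounds as given and uses the full 0.05.

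**Conclusion.** The concern holds. The plan promises an overall two-sided 0.05 over three efficacy looks, prints no final bound, and gives 0.05 as the only level for the primary test. Taken literally, overall error is about 0.056 instead of 0.05, given looks at 25/50/75% with the printed bounds and every crossing treated as a rejection. The range over the assumed timings is 0.0500 to 0.0595. If 0.05 was meant as the overall level, the fault is a missing decision threshold and not inflation. The probability that the ambiguity decides the result is low, between 0.6% and 1.4%, and the effect on the futility rule is minor. It should still be corrected, because it concerns the success criterion for the primary hypothesis.

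**What to change.** In SAP 7.7, state that 0.05 is the overall two-sided level for the primary hypothesis and that the final test uses the group-sequential alpha remaining after the interim looks. Give the value: two-sided p < 0.0438 if all three looks are held at 25/50/75% with the printed bounds. Add that otherwise the threshold is recomputed from the looks actually held and their actual information fractions.

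In SAP 7.4 and Protocol 6.3.3, add the final bound to the list of efficacy bounds, and say that conditional power uses the same final threshold. The 95% intervals in SAP 9.3 may stay for reporting, provided the success criterion is the adjusted threshold.

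The change is wording in three places. With the looks counted, power falls from about 80.6% to 79.2% at the 80% design size and from 90.4% to 89.4% at the 90% size. The 878 minimum would then sit slightly under 80%, and the plan should say so.

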## 7.8 Examination of Subgroups

Treatment heterogeneity by hospital center, gestational age, and sex will be examined as part of the primary analysis. If any interaction effects are determined to be significant, subgroup analysis will be performed to assess the treatment effects in the appropriate subpopulations. See Section 9.3 for more details.

#### 8 STUDY PARTICIPANT CHARACTERIZATION

#### 8.1 Participant Disposition

Participant eligibility status will be summarized, and overall disposition of study participants will be described using a standard CONSORT diagram. The number of participants randomized and those completing or discontinuing from study therapy will be summarized. Reasons for study withdrawal will be listed.

## **8.2 Protocol Deviations**

Protocol deviations will be listed with information such as type of deviation, time of occurrence, and reason. Depending on the number of deviations reported, the number of protocol deviations will also be summarized overall and for each protocol deviation category.

## 8.3 Study Drug Exposure and Compliance

Adherence to medication regimens is affected in a multi-factorial manner. A review of 51 studies with 19 chronic diseases found a wide range of factors for lack of compliance, falling within categories of socioeconomic, patient-related, and therapy-related determinants. The conclusion of this large systematic review points to the use of multiple methods to better attain compliance with medications at home.

For this trial, we will combine two recommended methods to assure adequate monitoring and improve compliance with medication administration:

- a. While the infant remains inpatient, the medication will be administered by the nurse as directed and the research nurse will perform a chart review at least twice a week to ensure study medication is being received after randomization and prior to discharge.
- b. After discharge:
  - i. A Medication form will be supplied to the parents. This will include a daily item to mark if medication was administered. In addition, parents can use this form to record sick visits to the Health Care Provider, emergency room, or hospitalizations as well as weights obtained during well-child or sick visits and missed doses of study medication. Any new medications prescribed will also be noted on this form.
  - ii. A Follow-up form will be supplied. This will be similar to the Medication form but will be used during the second four-week period discharge and will not include a medication administration section. Safety outcomes (such as Health Care Provider, Emergency visits, and re-admissions to a hospital) will be recorded on this form also.
  - iii. A member of the research team will contact the parents within the first 72 hours after discharge to answer questions and assess medication compliance.
  - iv. A member of the research team will contact the parents once a week during the first 4 weeks and biweekly during weeks 5-8 to address concerns and evaluate medication compliance\*. During this contact, the parents will be asked about any well or sick visits made to the health care provider, urgent care, emergency room, or hospital since the last contact and the reason for these visits.

\*To ensure both safety and compliance, vials will be marked with a number corresponding to the beginning day of medication to be administered at home. For example, the next day after discharge, the parent is to administer the study drug from the vial marked #1 by oral syringe. The following day, the vial marked #2 should be given. This procedure, using an oral syringe, should be followed until day 28 after discharge when the last medication vial marked #28 should be given. If a dose is missed, it may be given at any time on that day as long as it is given at least 12 hours before the next dose is due the next day. If it was not given at all, the parents will be instructed to discard the dose that was missed and record it on the medication form. The schedule of medication administration will then continue with the next numbered vial. This information will be noted for further analysis at the conclusion of the trial. Because of the long half-life of caffeine, single missed doses will have little clinical effect.

